Subsequent to the above-mentioned phase 1 study, a prospective longitudinal phase 2 study was initiated to evaluate the use of Gravid Ovipositing Sticky (GOS) trap and the NS1 testing system for surveillance of dengue virus transmission in urban Malaysia over a two-year period. The findings showed that dengue cases would occur lag one week after infected mosquitoes are obtained and will peak at lag of 2 to 3 weeks (30). These results showed that this proactive strategy is beneficial for dengue vector surveillance programme. The usage of the GOS trap which is simple to setup, cost effective (below USD 1 per trap) and environment friendly (i.e. use recyclable plastic materials) to capture *Ae. aegypti* followed by a rapid method of detecting of dengue virus using the NS1 dengue antigen kit has shown promising results. Control measures could be initiated when positive mosquitoes are detected, for example activity such as search and destroy breeding containers. This innovative usage of GOS trap coupled with NS1 detection in mosquito provides a comprehensive early warning and surveillance system that has the predictive capability for epidemic dengue.

6. Relevance to Government Policy, if any

This cluster randomised trial is expected to provide robust estimates of the intervention effects. A rigorous evaluation of these vector control interventions is vital to the development of an evidence-based control strategy and to help direct government resources in the right direction to reduce dengue epidemics.

7. Methodology

This is a community-based study assessing the knowledge, awareness and practice on dengue infection and its prevention. We choose PJU10 because it is the dengue 'hotspot' area according to local health council. We have identified a low-cost housing area with population of approximately 48700 people.

Sample size calculation:

Sample size for intervention trial:

To test for effectiveness of intervention in reducing dengue cases, on average, each housing unit will have 2% risk of dengue per year. A sample of 5710 unit (2855 per arm) will be required to achieve 80% power at alpha of 0.05 with the assumption of reduction in 50% of risk at the end of intervention. Eight apartments with 7979 residential units will be selected and randomised into intervention and control. Apartment will be the item of randomisation.

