To test for effectiveness of intervention to improve knowledge, assuming the knowledge in control group is 50% and knowledge in intervention is 70%, total sample calculated to achieve 80% power at alpha of 0.05, is 208 (104 per arm). After inflation of 20% sample required is 250 (125 per arm).

Sample size calculation for survey/cross-sectional study:

For prevalence study (knowledge), assuming baseline knowledge in population is 50%, total sample calculated to achieve 80% power at alpha of 0.05, is 384. After inflation of 20% sample required is 460.

For sero-prevalence study (blood), assuming baseline dengue sero-prevalence in population is 60%, total sample calculated to achieve 80% power at alpha of 0.05, is 369. After inflation of 20% sample required is 443.

According to the sample size calculation, the final sample size will be 500. Therefore, 250 in intervention group and 250 in the non-intervention group (control).

Phase I: KAP Questionnaire survey and blood taking

Pre-tested questionnaires will be distributed to members of community who have given consent to participate in this study.

Inclusion criteria:

- 1) All men and women aged above 18 years, including pregnant women.
- 2) Able to give consent
- 3) Willing to participate in blood taking

Exclusion criteria:

- 1) Age below 18 years
- 2) Unable to give consent
- 3) Not willing to give blood

After the questionnaire survey, 3 ml of venous blood will be taken to analyse for seroprevalence of dengue infection (dengue IgG and IgM will be carried out).

Phase II: Placement of GOS mosquito trap in the intervention group

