All clusters in intervention arm will receive the GOS traps. A maximum of 21 traps will be set per apartment block, on every third floor. The traps will be monitored weekly and the abdomen of *Aedes* obtained will be tested for dengue virus using the NS1 antigen test kit. If positive search and destroy measures will be conducted by the community under the supervision of community leader and the health staff. To identify the mosquito which carries the virus, dengue NS1 antigen tests will be carried out from the head and thorax of the individual mosquitoes from positive pool of mosquitoes. For the control clusters, routine dengue control and surveillance will be carried out as per the current Ministry of Health control activity, where no traps will be set, and dengue control measure will be initiated when human cases are reported from the control group. Data collection will be conducted for 1 year and 6 months.

When a positive mosquito is obtained, flyers and banners will be distributed and hung to inform the residents of the presence of dengue transmission in the apartment block/apartment. Alternatively, the residents may also be approached house-to-house or an educational booth set up at strategic locations in the apartment to warn and educate the residents.

Phase III: Repeat of KAP questionnaire

The KAP questionnaire survey will be repeated 15 months after intervention in the intervention arm.

Phase IV: Statistical Analyses

Data of serologically confirmed dengue cases (by NS1 or IgM/IgG) from the eight residential blocks will be obtained from the Selangor State Health Department, Malaysia. It is mandatory for all hospitals and private practitioners to report cases to the Ministry of Health. The date of onset of case will be used for all data analyses.

For analysing the change in level of dengue KAP, the mean of the percentage score of the population for each domain (knowledge & attitude/practises) will be determined for the pre- and post-questionnaire. Then, paired t-test will be performed to determine the presence of significant changes in both means. A p-value of at most 0.05 indicates a significant change/improvement in the mean score (An increase in score percentage indicate a better outcome). Additionally, an individual percentage score of 80% and above indicates good knowledge/attitude/practice. Accordingly, chi-squared test will be used to determine the extent to which good knowledge is related to good attitudes/practises

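### The knowledge sample size has no allowance for clustering and the planned pre-post paired t-test ignores correlation within apartments, so its p-values can be too small and the stated 80% power is not assured

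*Combined protocol and SAP*

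**What the plan says.** All references are to section 7, Methodology, of the combined protocol and SAP.

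- **Unit of randomisation** (sample size for the intervention trial): "Eight apartments with 7979 residential units will be selected and randomised into intervention and control", and "Apartment will be the item of randomisation". The split of the eight between arms is not given.
- **Knowledge sample size** (same subsection): "assuming the knowledge in control group is 50% and knowledge in intervention is 70"%, giving "total sample calculated to achieve 80% power at alpha of 0.05, is 208 (104 per arm"). Then "After inflation of 20% sample required is 250 (125 per arm"). The reason for the 20% is not stated. No ICC, design effect or number of apartments enters the calculation.
- **Final survey size** (sample size for the survey): "According to the sample size calculation, the final sample size will be 500", that is, "250 in intervention group and 250 in the non-intervention group (control"). The two prevalence calculations just above it give 460 and 443 after inflation.
- **Repeat survey** (Phase III): the questionnaire is repeated at 15 months in the intervention arm only. The executive summary agrees.
- **KAP analysis** (Phase IV): pre and post mean percentage scores are compared, and a "paired t-test will be performed to determine the presence of significant changes in both means". A chi-squared test then relates good knowledge to good attitudes and practices. The only mixed model in the plan is for weekly mosquito and case counts.

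**The concern.** Flyers, banners, booths and search-and-destroy are triggered when a positive mosquito is found in a particular block or apartment. How much education residents receive therefore depends on where they live, and changes in score within an apartment can be expected to move together. A paired t-test on 250 respondents treats them as 250 independent pieces of evidence, when about four apartments stand behind the result. A shift confined to one or two apartments could then be declared significant.

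The sample size has the same gap. Community receptiveness is one of the trial's two objectives, and the only power statement for a KAP comparison between arms assumes that respondents were randomised one by one.

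**Working it through.** **Inputs.** From the protocol: 50% v 70%, alpha 0.05, 80% power, 104 per arm, 250 per arm in the final survey, eight apartments. Assumed, because the documents are silent: a two-sided test, four apartments per arm, equal numbers per apartment, the same respondents surveyed twice, and ICCs from 0.01 to 0.05.

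**Step 1. Reproduce 104 per arm.** Two-sided comparison of two proportions, pooled variance under the null:

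n0 = [1.96 × √(2 × 0.6 × 0.4) + 0.842 × √(0.25 + 0.21)]² / 0.20² = 93.0

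With continuity correction: n = (93.0/4) × [1 + √(1 + 4/(93.0 × 0.20))]² = 102.8, so 103 per arm (206 in total) against the plan's 104 (208). The one-sided versions give 74 or 83. The figure is sound arithmetic for independent respondents. The inflation is 208 × 1.2 = 249.6, or 250.

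**Step 2. Power with clustering.** Design effect DE = 1 + (m − 1) × ICC, with m = n/4 per apartment. Effective n = n/DE. SE = √(0.46/effective n). Power is for a difference of 0.20, by a normal test (unpooled variance) and by a noncentral t on 8 − 2 = 6 df.

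| n per arm | m | ICC | DE | Effective n | Power, normal | Power, 6 df |
|---|---|---|---|---|---|---|
| 104 | 26 | 0.01 | 1.25 | 83.2 | 77% | 61% |
| 104 | 26 | 0.05 | 2.25 | 46.2 | 52% | 39% |
| 250 | 62.5 | 0.01 | 1.62 | 154.8 | 96% | 86% |
| 250 | 62.5 | 0.02 | 2.23 | 112.1 | 88% | 74% |
| 250 | 62.5 | 0.05 | 4.08 | 61.3 | 64% | 49% |

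At 104 per arm, power on 6 df is 71% even with an ICC of zero.

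**Step 3. Where 80% power ends at 250 per arm.** The normal test (pooled variance) needs an effective 93.0 per arm: DE = 250/93.0 = 2.69, so ICC = 1.69/61.5 = 0.027 (0.029 with the unpooled variance). The 6-df test needs 130.4: DE = 1.92, so ICC = 0.92/61.5 = 0.015.

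With four apartments, effective n cannot exceed 4/ICC. An effective 104 is therefore out of reach for any number of respondents once the ICC reaches 4/104 = 0.038.

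**Step 4. Type I error of the planned paired t-test.** With 250 respondents in four apartments, the true variance of the mean change is DE times what the test assumes. The approximate error is 2 × [1 − Φ(1.96/√DE)].

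| ICC of change score | DE | Formula | Simulated |
|---|---|---|---|
| 0.01 | 1.62 | 12% | 12% |
| 0.02 | 2.23 | 19% | 19% |
| 0.05 | 4.08 | 33% | 33% |

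In simulation, a t-test on the four apartment mean changes (3 df) stays at about 5% throughout.

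**Step 5. Match power to analysis.** The 50% v 70% figures compare arms. Phase III collects follow-up KAP data in one arm only, and Phase IV compares pre with post. The powers in Step 2 therefore describe a test that is not planned, while Step 4 describes the one that is.

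**The case against.** **The survey enrols 500, not 208.** This stands in part. The final size is 2.4 times the stated need (500/208), and at an ICC of 0.01 power is 96% or 86%. A reader might infer that the 80% power is simply lost. The documents do not support that: they give no ICC, and at a small one the power holds. The larger survey does not help the paired t-test, though. More respondents in the same apartments make its error worse: at an ICC of 0.02 it is 12% with 125 respondents and 19% with 250.

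**No between-arm KAP test is planned.** True. It makes the stated power irrelevant to the planned analysis, but it does not protect the pre-post p-value.

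**The chi-squared test.** A reader might infer that it too gives p-values that are far too small. That does not follow. It examines an association between two answers from the same person, not a contrast between arms or times. Its error is inflated only if both answers cluster by apartment, which the documents do not show. In simulation with independent apartment effects on both answers, its error was about 5% to 7% at ICCs of 0.01 to 0.05.

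**A mixed model with apartment and respondent intercepts would be enough.** It would not. Those intercepts cancel out of a pre-post change. In one simulated data set of four apartments with 62 respondents each, that model and the paired t-test both gave a standard error of 0.0660; apartment mean changes gave 0.221.

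**Conclusion.** The point holds in this form. The 208 (104 per arm) makes no allowance for clustering, and the planned paired t-test is anti-conservative if changes correlate within apartments: about 12%, 19% and 33% true error at ICCs of 0.01, 0.02 and 0.05. The 80% power is not assured rather than absent, and it is attached to a comparison that the plan does not make. The sizes rest on four apartments per arm, equal cluster sizes and assumed ICCs. Neither the chi-squared test nor an outright loss of power is part of the conclusion.

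**What to change.** 1. Replace the respondent-level paired t-test with a one-sample t-test on apartment mean changes (3 df with four apartments). Alternatively, use a linear mixed model with a respondent effect and an apartment-by-time random effect, with small-sample degrees of freedom. State that random intercepts alone do not correct the standard error.
2. State the number of apartments per arm and that the 208 (104 per arm) does not allow for clustering.
3. Restate KAP power for the pre-post test actually planned, over a range of ICCs. This needs an assumed standard deviation of the change score, which the documents do not give.
4. Either drop the 50% v 70% between-arm power statement or specify the comparison that it serves. The latter would need follow-up KAP data in the control arm, which is a separate design decision.
5. Leave the chi-squared test as it is.

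Items 1 to 3 need only SAP wording and a different analysis of the same questionnaires, with no extra respondents. The price is wider intervals and a lower stated power, and the 3-df test is demanding: its two-sided critical value is 3.18, against about 1.97 for the respondent-level test.

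### The chi-squared test on scores cut at 80% cannot show how strongly knowledge and attitude/practice are related, and the cut discards information the plan already has (minor)

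*Combined protocol and SAP*

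**What the plan says.** The relevant text is in section 7, Methodology, under Phase IV (Statistical Analyses) of the combined protocol and SAP.

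- **Scores.** For the pre- and post-questionnaire, "the mean of the percentage score of the population for each domain (knowledge & attitude/practises) will be determined". The change in means is tested by a paired t-test on the uncut scores.
- **Cut.** As an additional analysis, "an individual percentage score of 80% and above indicates good knowledge/attitude/practice". No reason is given for the 80% threshold.
- **Association.** On those categories, a "chi-squared test will be used to determine the extent to which good knowledge is related to good attitudes/practises".

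No odds ratio, risk difference, phi coefficient, correlation or confidence interval is named for this question, here or in the modelling text that follows.

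On numbers, the sample size part of section 7 says "the final sample size will be 500", split 250 and 250. Under Phase III, "The KAP questionnaire survey will be repeated 15 months after intervention in the intervention arm", so the repeat survey has at most about 250 respondents. The plan does not say whether the association is to be examined in the first survey, the repeat, or both.

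**The concern.** The stated question is how far knowledge goes with attitude and practice. The stated method answers a different one: whether the data are compatible with no association at all. A p-value from that test cannot be read as strength, and it is not comparable between a survey of 500 and a repeat of about 250.

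The test is also run after both scores are reduced to yes or no. A respondent at 79% is then treated like one at 20%, although the percentage scores exist for every completed questionnaire.

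The intervention relies on informed residents acting on warnings, so readers will want to know whether knowledge goes with practice. A significant result without an effect size does not tell them how much. A non-significant result at low power could be misread as knowledge not carrying over into practice.

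**Working it through.** **Is there a figure in the plan to reproduce?** Not for this analysis. The nearest is the knowledge comparison between arms, "assuming the knowledge in control group is 50% and knowledge in intervention is 70" per cent, with 104 per arm at 80% power and alpha 0.05. Taking a two-sided test:

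- Uncorrected: n = [1.960·√(2·0.6·0.4) + 0.8416·√(0.5·0.5 + 0.7·0.3)]² / 0.2² = (1.358 + 0.571)² / 0.04 ≈ 93 per arm.
- With continuity correction: (93/4)·[1 + √(1 + 4/(93·0.2))]² ≈ 103 per arm.

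The stated 104 is within one of the corrected figure. It concerns a difference between arms and does not bear on the association.

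**Step 1: strength and sample size are mixed.** For a 2×2 table, chi-squared = n·φ², where φ is the phi coefficient. With φ = 0.15:

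- n = 125: 125 × 0.0225 = 2.81, p = 0.094
- n = 250: 250 × 0.0225 = 5.63, p = 0.018
- n = 500: 500 × 0.0225 = 11.25, p = 0.0008

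Conversely, p = 0.05 corresponds to φ = 1.96/√n, which is 0.175, 0.124 and 0.088 at those sizes.

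**Step 2: information lost by the cut.** Assumed, because the documents are silent: bivariate-normal scores, independent respondents, and shares p and q scoring 80% or more in the two domains. Near zero correlation, the efficiency of the 2×2 test relative to the Pearson correlation is f(p)·f(q). Here f(p) = d(z)² / [p(1−p)], where d is the standard normal density at the cut z. This gives f(0.5) = 0.637, f(0.7) = 0.576, f(0.2) = 0.490 and f(0.1) = 0.342.

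| Shares good | Efficiency | Loss | 500 respondents count as |
|---|---|---|---|
| 50% / 50% | 0.637 × 0.637 = 0.405 | 59.5% | about 203 |
| 50% / 70% | 0.637 × 0.576 = 0.367 | 63.4% | about 183 |
| 50% / 20% | 0.637 × 0.490 = 0.312 | 68.8% | about 156 |
| 20% / 20% | 0.490 × 0.490 = 0.240 | 76.0% | about 120 |
| 10% / 10% | 0.342 × 0.342 = 0.117 | 88.3% | about 59 |

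The loss is symmetric, so a share of 90% loses as much as one of 10%. With equal shares, it stays at or below 70% only when both lie between about 26% and 74%.

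**Step 3: what this does to power.** Under the same assumptions, at two-sided 0.05, power for the uncut scores is Φ(atanh(ρ)·√(n−3) − 1.960). Power for the test on the table is very nearly Φ(√n·φ − 1.960), with φ obtained from the bivariate normal. Example with n = 250 and ρ = 0.20:

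- Scores: 0.2027 × √247 = 3.186, and Φ(1.226) = 89%.
- Table at 50%/50%: φ = (2/π)·arcsin(0.20) = 0.128. √250 × 0.1282 = 2.027, and Φ(0.067) = 53%.
- Table at 50%/20%: φ = 0.112. √250 × 0.1119 = 1.769, and Φ(−0.191) = 42%.

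| n | ρ | Scores | Table, 50/50 | Table, 50/20 |
|---|---|---|---|---|
| 500 | 0.15 | 92% | 57% | 47% |
| 250 | 0.20 | 89% | 53% | 42% |
| 250 | 0.30 | above 99% | 87% | 76% |
| 500 | 0.30 | above 99% | 99% | 96% |

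At ρ = 0.40 the table has at least 94% power for these cuts at either size. For extreme shares the loss bites at stronger correlations too. At 10%/10% and ρ = 0.30, φ = 0.129, √250 × 0.129 = 2.040, and power is Φ(0.080) = 53%. In sample size terms, ρ = 0.30 needs about 85 respondents for 80% power with the scores, against 209 (50/50), 294 (20/20) or 471 (10/10) with the table.

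**The case against.** The best defence has four parts.

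- **The table already contains an effect size.** Proportions, an odds ratio or phi can be read from the planned 2×2 table, and nothing forbids reporting them. This stands. A reader might infer that the trial will be unable to say how large the association is. The documents do not support that: the plan fails to name a measure, but the data will allow one.
- **The question is about categories.** The plan defines good as 80% or more and asks about good knowledge and good attitude/practice. A correlation describes the whole score range, which is a somewhat different question. This stands too, and is the reason to keep the table alongside.
- **The loss is not a figure from the plan.** A reader might infer that the cut is known to discard 60–70% of the information. It is not. The documents give no score distribution, no share reaching 80% and no expected correlation. The 50% and 70% in the sample size text are not said to be shares scoring 80% or more. Bounded questionnaire scores may be skewed or pile up at the top. Under normality about 60% is a floor, and 70% is not a ceiling.
- **Power may be adequate.** At moderate shares and a correlation of 0.30 or more, the planned test does reasonably well. A reader might infer that it will probably miss a real association. That follows only if the correlation is weak or the shares are extreme, and the documents give no reason to expect either.

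None of this answers the basic point that the method named does not deliver the quantity asked for.

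**Conclusion.** The concern holds in a limited form. A chi-squared test is assigned to determine the extent of a relation and cannot do so alone, and no effect measure or interval is specified. This part needs no assumption. The cut at 80% also gives up information for no stated reason. Its size rests on bivariate-normal scores, independent respondents and assumed shares: about 60% at the least, about 69% at 50%/20%, and about 88% at 10%/10%. The power figures ignore clustering by apartment for both methods.

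The severity is minor. A reader might infer that the trial's assessment of KAP change, or of the intervention, is compromised. It is not: the paired t-test uses uncut means, the case and mosquito models are untouched, and a knowledge–practice association is in neither of the two objectives in section 3.

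**What to change.** In Phase IV, make the main measure of this relation the correlation between the two percentage scores, or the regression slope of the attitude/practice score on the knowledge score, with a 95% confidence interval allowing for apartment. Use Spearman's correlation if the scores are skewed or show a ceiling. With only eight apartments, terms for apartment in the model are safer than cluster-robust standard errors. Keep the 80% table as a descriptive companion with an odds ratio and 95% confidence interval. State whether the analysis uses the first survey, the repeat, or both.

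The cost is a few sentences of SAP text, with no new data and no change in sample size. The one small downside is that a correlation or slope describes the whole score range, not the good categories; keeping the table covers that.

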All statistical analyses will be done using weekly data and R programming language for statistical analysis (version 3.2.4) (30). The family of distributed lag non-linear models (DLNM), (*DLNM* package version 2.20), which can simultaneously analyse non-linear factor-response dependencies and delayed effects, and provides an estimate of the overall effect in the presence of delayed contributions will be utilised. For dengue cases and its relation to dengue-positive *Aedes* pool, the model to be used will be: `glm(case ~ cb.total_aedes + cb.ns1positive + ns(time, 3) + woy, family = quasipoisson, data)` where `woy` = week of the year. Both the *Ae. aegypti* / *Ae. albopictus* trapped per week and cases per week at each apartment will be analysed by generalised linear mixed model (GLMM). Zero inflation and Poisson distribution were incorporated in the analysis. Differences in numbers of *Ae. aegypti* and cases between blocks and between floors were tested with Tukey's contrasts at $P = 0.05$.

References

1. Gubler, D.J., and Clark, G.G. (1995). Dengue/dengue hemorrhagic fever: the emergence of a global health problem. *Emerg Infect Dis* 1, 55.
4. Faria NR, da Silva Azevedo RS, Kraemer MU, Souza R, Cunha MS, Hill SC, et al. (2016). Zika virus in the Americas: Early epidemiological and genetic findings. *Science* 352(6283):345-9.

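### The distributed-lag model has no apartment term and no stated data structure: stacking apartment-weeks can create a false pool-to-case link, and summing apartments dilutes a true one

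*Combined protocol and SAP*

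**What the plan says.** Phase IV: Statistical Analyses introduces the model with "For dengue cases and its relation to dengue-positive *Aedes* pool, the model to be used will be" and then gives the formula "glm(case ~ cb.total_aedes + cb.ns1positive + ns(time, 3) + woy, family = quasipoisson, data". Its terms are lag cross-bases for total Aedes and for positive pools, a time spline and week of year. There is no apartment term, random effect or offset for units or residents.

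The section also says "All statistical analyses will be done using weekly data". It does not define `data`, name the apartments that enter, or give the cross-basis settings (maximum lag, degrees of freedom, grouping). Apartments appear as a level of analysis only in the next model, where "cases per week at each apartment will be analysed by generalised linear mixed model (GLMM". That model covers Aedes counts and case counts; it is not described as including positive pools.

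The sample size section says "Eight apartments with 7979 residential units will be selected and randomised into intervention and control" and does not give the size of each apartment. Phase II says "All clusters in intervention arm will receive the GOS traps", with up to 21 traps per block. In the control clusters the plan is routine activity, "where no traps will be set". A positive mosquito triggers an alert in the block or apartment where it was found.

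**The concern.** Pool data exist only for the intervention apartments, so the model must handle several weekly series side by side. The formula allows two ways of doing so, and each has a cost.

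- **Stacked apartment-weeks.** A larger apartment can have more traps, more mosquitoes, more positive pools and more cases. Without an apartment term, this difference between apartments enters the lag coefficients and can look like early warning.
- **One summed series.** Fixed size differences drop out, but a pool in one apartment is then set against cases in all of them, although the alert and response are local.

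The early-warning claim (Literature Review: cases begin one week after infected mosquitoes are found and peak at 2 to 3 weeks) is tested in this trial by no other stated model. Two analysts could follow the same text and reach opposite answers.

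**Working it through.** The plan states no figure for this model, so there is none to reproduce. The check is by simulation.

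**Inputs from the plan**
- 8 apartments and 7979 units; traps in the intervention arm only.
- 1 year 6 months of data: 1.5 × 52 = 78 weeks.
- 2% dengue risk per unit-year (sample size section).

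**Assumptions**
- Equal split: 4 trapped apartments, 7979/2 ≈ 3990 units, mean 997 each. Mean cases per apartment-week: 997 × 0.02/52 = 0.38.
- Mean catch 8 Aedes and 0.4 positive pools per apartment-week, both proportional to apartment size.
- Lags 0 to 4 weeks, quadratic in lag and linear in exposure; `woy` as a linear term.
- Sizes: 2:1 (668, 828, 1167, 1327 units), 3:1 (499, 798, 1197, 1496) and 6:1 (299, 698, 1197, 1795).

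**Step 1: no true link.** Quasi-Poisson GLM with both lag bases, joint F test of the positive-pool basis at 0.05, 1000 runs per row, negative binomial catches with dispersion k = 3. False-positive rates:

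| Largest : smallest | Stacked, lags crossing apartments | Stacked, lags within apartments | Within-apartment lags plus apartment term | Summed series |
|---|---|---|---|---|
| 1:1 | 4.9% | 4.7% | 4.6% | 4.0% |
| 2:1 | 9.6% | 8.5% | 5.1% | 4.2% |
| 3:1 | 11.1% | 11.9% | 4.4% | 3.7% |
| 6:1 | 21.6% | 20.9% | 4.7% | 4.2% |

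The Monte Carlo standard error near 5% is √(0.05 × 0.95/1000) = 0.7 points.

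**Step 2: sensitivity to catch noise.** Total Aedes is in the plan's formula and acts as a partial proxy for size. How well it does so depends on how noisy the catch is.
- Noisier catches (k = 1, 500 runs): the stacked formula gave 8.8%, 14.2% and 34.8% at 2:1, 3:1 and 6:1, with median spurious cumulative rate ratios of 1.20, 1.45 and 1.74. With the apartment term and grouped lags it was 5% to 6%, with a ratio of about 0.97.
- Poisson catches (low noise): close to nominal, 2% to 7% across runs.

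**Step 3: lag spill-over.** Stacking gives 4 × 78 = 312 rows. With lags to 4 weeks, 3 joins × 4 rows = 12 rows (12/312 = 3.8%) could draw a lag from another apartment. The first two columns of the table differ little, so the missing apartment term drives the inflation.

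**Step 4: a true within-apartment link, equal sizes.**

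| True cumulative RR per pool | Summed: estimate, power | Apartment-level: estimate, power |
|---|---|---|
| 1.82 | 1.16, 13% | 1.76, 39% |
| 2.46 | 1.28, 22% | 2.38, 76% |

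A second set of runs at a true ratio of 1.8 gave about 1.2 with 15% power, against 53% at apartment level. Simple arithmetic agrees. With four equal apartments, a pool in one of them acts on a quarter of the cases, so a true ratio of 1.82 becomes about 1.82^(1/4) = 1.16 on the log scale, or 1 + 0.82/4 = 1.21 on the additive scale.

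**The case against.** The best defence is that the formula describes one area-wide series. It has a single time spline and no unit index, and the plan speaks of each apartment only when it turns to the GLMM. On that reading size cannot confound, and the simulated false-positive rate is 3.7% to 4.2%. An area-wide early-warning association is a legitimate question, and the plan does not say that the link is sought within each apartment. This stands as far as bias under the null goes. It does not answer the dilution in Step 4, and it sits poorly with alerts that are local.

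A reader might infer three stronger things, none of which the documents support.

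- **That the model lets lags run from one apartment into the next.** Grouping is set when the cross-bases are built, and the plan does not show that step. It is unspecified, not shown to be wrong, and its effect is small.
- **That a false association is to be expected.** This needs stacked rows, unequal apartments and noisy catches together. The plan fixes none of the three. A simulation that leaves out total Aedes would overstate the inflation, because that term is in the formula.
- **That the trial's arm comparison is affected.** This model does not compare arms; cases per apartment go to the GLMM.

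**Conclusion.** The concern holds in a conditional form. As written, the model permits two data structures, and each does worse than a simple alternative. With stacked rows and total Aedes included, the false-positive rate runs from about 5% (low-noise catches) to 20% to 35% (overdispersed catches, 6:1 size ratio). With a summed series it stays near 5%, but a true cumulative rate ratio of 1.8 shrinks to about 1.2, with power of about 15% against 40% to 50%. The apartment-level model avoids both problems.

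The figures rest on assumed apartment sizes, catch and pool rates, an equal split of apartments and a 0 to 4 week lag. They show direction and plausible range and do not forecast this trial's result. The change should be made because the early-warning claim depends on this model; the randomised comparison does not.

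**What to change.** In Phase IV, state that the distributed-lag model is fitted to apartment-by-week rows from the intervention apartments only. Add apartment as a fixed effect to the formula. Build `cb.total_aedes` and `cb.ns1positive` with apartment as the group, so that lags restart in each series, and state the maximum lag and lag basis. The fixed effect absorbs any size difference that is constant over follow-up. If an area-wide association is also wanted, name the summed series as a separate, secondary analysis and list the apartments in it.

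The cost is SAP wording and two code changes: about 3 degrees of freedom with four apartments, and the first few weeks of each series (with lags to 4 weeks, 4 × 4 = 16 of 312 rows). No new data are needed. If the apartments prove equal in size the loss is slight: at a true ratio of 2.46, power was 76% against 78% for the stacked model without the term.
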